Suicide attempt	Any episode of suicide attempt and suicide related codes, including deliberate medication overdose
Other chronic psychiatric conditions	Eating disorders, body image disorder, attention-deficit disorder (ADHD), behavioural disorders, adjustment disorder, acute stress disorder, schizophrenia, bipolar disorder and post-traumatic stress disorder (PTSD)
Others	Problems with sleep

*this excludes conditions which are potentially single events i.e. self-harm or suicide attempt. (See Appendix 1 – Table s3 for Read Codes and SNOMED Codes

for mental health conditions, Table s4 for mental health condition algorithms and Table s5 for WHO ICD-10 mental health conditions).

Stream 1: Incidence of mental health conditions

The study will report the incidence of each mental health condition overall in the PIBD cases and controls, and adjusted hazard ratios to test the association between PIBD and risk of the same mental health conditions. Within the PIBD cohort we will examine the relationship between PIBD age of onset, sex, ethnicity, and social deprivation and the 'any psychological condition' composite outcome.

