Read CTV3 Code	Term ID	Description
SNOMED Code	Term ID	Description

sTable 2.2 Algorithms used to identify anxiety episodes, depression episodes, and recurrent major depression. Expressions in capitals equate to Boolean expressions. *More than 1 year ago. SSRIs = selective serotonin reuptake inhibitors, TCA = tricyclic antidepressants, MAOI = monoamine oxidase inhibitors, CBT = cognitive behavioural therapy.

Clinical entity	Definition
Anxiety	Any coded anxiety episode AND concurrent treatment for anxiety
Depressive episode	Any coded depressive episode AND concurrent treatment for depression
Recurrent depressive disorder	(Any historical code* for a depressive episode AND current treatment for depression) OR Any code for recurrent depressive disorder
Anxiety treatments	SSRIs, anxiolytics, counselling, CBT, and psychotherapy
Depression treatments	SSRIs, TCAs, MAOIs, counselling, CBT, and psychotherapy

sTable 2.3 WHO International Statistical Classification of Diseases (ICD-10) for mental health conditions

Clinical entity	ICD 10 code	Definition
Depressive episode	F32	Any coded depressive episode AND concurrent treatment for depression
Recurrent depressive disorder	F33	(Any historical code* for a depressive episode AND current treatment for depression) OR Any code for recurrent depressive disorder
Depression treatments	NA	SSRIs, TCAs, MAOIs, counselling, CBT, and psychotherapy
Anxiety	F41	Any coded anxiety episode AND concurrent treatment for anxiety
Anxiety treatments	NA	SSRIs, anxiolytics, counselling, CBT, and psychotherapy
Self-harm	X60-X84	Any diagnostic or indicative code for any form of self-harm, including suicide attempt
Eating disorders	F50	Any diagnostic or indicative code for eating disorders

Body image disorders	F45.2	Any diagnostic or indicative code for body image / dysmorphic disorder (excluding hypochondriacal disorders not associated with body image)
Attention-deficit disorders	F90.0	Any diagnostic or indicative code for disturbance of activity and attention
Behavioural disorders	F91 F92	Any diagnostic or indicative code for conduct disorders
Adjustment disorders	F43.2	Any diagnostic or indicative code for adjustment disorders
Acute stress disorders	F43.0	Any diagnostic or indicative code for acute stress disorders
Post-traumatic stress disorder	F43.1	Any diagnostic or indicative code for Post-traumatic stress disorder

Appendix 3

sTable 3.1 Read and SNOMED codes to be used to identify quality of life

Depressive episode		

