U243.	All	[X]Intentional self harm by rifle, shotgun and larger firearm discharge, occurrence at sports and athletics area
U244.	All	[X]Intentional self harm by rifle, shotgun and larger firearm discharge, occurrence on street and highway
U245.	All	[X]Intentional self harm by rifle, shotgun and larger firearm discharge, occurrence at trade and service area
U246.	All	[X]Intentional self harm by rifle, shotgun and larger firearm discharge, occurrence at industrial and construction area
U247.	All	[X]Intentional self harm by rifle, shotgun and larger firearm discharge, occurrence on farm
U24y.	All	[X]Intentional self harm by rifle, shotgun and larger firearm discharge, occurrence at other specified place
U24z.	All	[X]Intentional self harm by rifle, shotgun and larger firearm discharge, occurrence at unspecified place

U25..	All	[X]Intentional self harm by other and unspecified firearm discharge
U250..	All	[X]Intentional self harm by other and unspecified firearm discharge, occurrence at home
U251..	All	[X]Intentional self harm by other and unspecified firearm discharge, occurrence in residential institution
U252..	All	[X]Intentional self harm by other and unspecified firearm discharge, occurrence at school, other institution and public administrative area
U253..	All	[X]Intentional self harm by other and unspecified firearm discharge, occurrence at sports and athletics area
U254..	All	[X]Intentional self harm by other and unspecified firearm discharge, occurrence on street and highway
U255..	All	[X]Intentional self harm by other and unspecified firearm discharge, occurrence at trade and service area
U256..	All	[X]Intentional self harm by other and unspecified firearm discharge, occurrence at industrial and construction area
U257..	All	[X]Intentional self harm by other and unspecified firearm discharge, occurrence on farm
U25y..	All	[X]Intentional self harm by other and unspecified firearm discharge, occurrence at other specified place
U25z..	All	[X]Intentional self harm by other and unspecified firearm discharge, occurrence at unspecified place
2...	All	[X]Suicide
TK...	All	Attempted suicide
TK0..	All	Suicide and selfinflicted poisoning by solid and liquid substances
TK00..	All	Suicide and selfinflicted poisoning by analgesics, antipyretics and anti-rheumatics
TK01..	All	Suicide + selfinflicted poisoning by barbiturates
TK010	All	Suicide and self inflicted injury by Amylobarbitone
TK011	All	Suicide and self inflicted injury by Barbitone

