TK012	All	Suicide and self inflicted injury by Butabarbitone
TK013	All	Suicide and self inflicted injury by Pentobarbitone
TK014	All	Suicide and self inflicted injury by Phenobarbitone
TK015	All	Suicide and self inflicted injury by Quinalbarbitone
TK01z	All	Suicide and self inflicted injury by barbiturates
TK02.	All	Suicide and selfinflicted poisoning by other sedatives and hypnotics
TK03.	All	Suicide and selfinflicted poisoning by tranquillisers and other psychotropic agents
TK04.	All	Suicide and selfinflicted poisoning by other drugs and medicines
TK05.	All	Suicide + selfinflicted poisoning by drug or medicine NOS
TK06.	All	Suicide and selfinflicted poisoning by agricultural and horticultural chemical and pharmaceutical preparations other than plant foods and fertilizers
TK07.	All	Suicide and selfinflicted poisoning by corrosive and caustic substances
TK08.	All	Suicide and selfinflicted poisoning by arsenic and its compounds
TK0z.	All	Suicide and selfinflicted poisoning by solid and liquid substances NOS
TK1..	All	Suicide + selfinflicted poisoning by gases in domestic use
TK10.	All	Suicide and selfinflicted poisoning by gas distributed by pipeline
TK11.	All	Suicide and selfinflicted poisoning by liquefied petroleum gas distributed in mobile containers
TK1y.	All	Suicide and selfinflicted poisoning by other utility gas
TK1z.	All	Suicide and selfinflicted poisoning by gases in domestic use NOS
TK2..	All	Suicide and selfinflicted poisoning by other gases and vapours
TK20.	All	Suicide and selfinflicted poisoning by motor vehicle exhaust gas
TK21.	All	Suicide and selfinflicted poisoning by other carbon monoxide
TK2y.	All	Suicide and selfinflicted poisoning by other gases and vapours
TK2z.	All	Suicide + selfinflicted poisoning by gases and vapours NOS
TK3..	All	Suicide and selfinflicted injury by hanging, strangulation and suffocation

TK31.	All	Suicide and selfinflicted injury by suffocation by plastic bag
TK3y.	All	Suicide and selfinflicted injury by other means of hanging, strangulation and suffocation
TK3z.	All	Suicide and selfinflicted injury by hanging, strangulation and suffocation NOS
TK4..	All	Suicide and selfinflicted injury by drowning
TK5..	All	Suicide and selfinflicted injury by firearms and explosives
TK50.	All	Suicide and selfinflicted injury by handgun
TK51.	All	Suicide and selfinflicted injury by shotgun
TK52.	All	Suicide and selfinflicted injury by hunting rifle
TK53.	All	Suicide and selfinflicted injury by military firearms

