Xa3jD	All	Attempted suicide - suffocation
Xa3jM	All	Suicide - suffocation

TK0..	All	Suicide and selfinflicted poisoning by solid and liquid substances
TK0z.	All	Suicide and selfinflicted poisoning by solid and liquid substances NOS
TK4..	All	Suicide and selfinflicted injury by drowning
TK5..	All	Suicide or selfinflicted injury by firearms and explosives
TK50.	All	Suicide or selfinflicted injury by handgun
TK51.	All	Suicide or selfinflicted injury by shotgun
TK52.	All	Suicide or selfinflicted injury by hunting rifle
TK53.	All	Suicide or selfinflicted injury by military firearm
TK54.	All	Suicide and selfinflicted injury by other firearm
TK55.	All	Suicide or selfinflicted injury by explosives
TK5z.	All	Suicide and selfinflicted injury by firearms and explosives NOS
Xa3jF	All	Attempted suicide - firearms
Xa3jO	All	Suicide - firearms
TK6..	All	Suicide or selfinflicted injury by cutting and stabbing
TK60.	All	Suicide or selfinflicted injury by cutting
TK61.	All	Suicide or selfinflicted injury by stabbing
TK6z.	All	Suicide and selfinflicted injury by cutting and stabbing instruments NOS
Xa3jG	All	Attempted suicide - cut/stab
Xa3jP	All	Suicide - cut/stab
TK7..	All	Suicide or self injury by jumping from a height
TK70.	All	Suicide and selfinflicted injury by jumping from residential premises
TK71.	All	Suicide and selfinflicted injury by jumping from other man-made structure
TK72.	All	Suicide and selfinflicted injury by jumping from natural sites
TK72.	All	Suicide and selfinflicted injury by jumping from natural sites
TK7z.	All	Suicide and selfinflicted injury by jumping from high place NOS
X71B6	All	Suicide or self injury by jumping from high man-made structure

X71B7	All	Suicide or self injury by jumping from high building
X71B8	All	Suicide or self injury by jumping from bridge
X71B9	All	Suicide or self injury by jumping from high natural feature
X71BA	All	Suicide or self injury by jumping off cliff
Xa3jH	All	Attempted suicide - jumping from a high place
Xa3jQ	All	Suicide - jumping from a high place
TKx..	All	Suicide and selfinflicted injury by other means
TKx0.	All	Suicide and selfinflicted injury by jumping or lying before moving object
TKx00	All	Suicide and selfinflicted injury by jumping before moving object
TKx01	All	Suicide and selfinflicted injury by lying before moving object
TKx0z	All	Suicide and selfinflicted injury by jumping or lying before moving object NOS
TKxy.	All	Suicide and selfinflicted injury by other specified means

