Ua14T	All	Throwing self in front of train
X71B0	All	Self poisoning by non-drug solid or liquid agents
TK07.	All	Self poisoning by corrosive or caustic substance
TK08.	All	Self poisoning by arsenic or its compounds
X71B2	All	Self poisoning by plants or parts of plants
XM1FX	All	Self poisoning by agricultural chemical
TK06.	All	Suicide and selfinflicted poisoning by agricultural and horticultural chemical and pharmaceutical preparations other than plant foods and fertilizers
X71B1	All	Self poisoning by paraquat
Ua14R	All	Shooting self
Xa2pL	All	Stabbing self
U21..	All	[X]Intent self harm by hanging, strangulation/suffocation
U210.	All	[X]Int self harm by hanging, strangulation/suffocation occ home
U211.	All	[X]Intent self harm by hanging, strangulation/suffocation at res institut
U212.	All	[X]Int self harm by hanging, strangulation/suffocation in school/pub admin area
U213.	All	[X]Intent self harm by hanging, strangulation/suffocation in sport/athletic area
U214.	All	[X]Int self harm by hanging, strangulation/suffocation in street/highway

U215.	All	[X]Intent self harm by hanging, strangulation/suffocation trade/service area
U216.	All	[X]Int self harm by hanging, strangulation/suffocation indust/construct area
U217.	All	[X]Int self harm by hanging, strangulation/suffocation occ farm
U21y.	All	[X]Int self harm by hanging, strangulation/suffocation other spec place
U21z.	All	[X]Intent self harm by hanging, strangulation/suffocation unspecif place
U22..	All	[X]Intent self harm by drowning and submersion
U220.	All	[X]Int self harm by drowning and submersion occ home
U221.	All	[X]Intent self harm by drowning and submersion at res institut
U222.	All	[X]Int self harm by drowning and submersion in school/pub admin area
U223.	All	[X]Intent self harm by drowning and submersion in sport/athletic area
U224.	All	[X]Int self harm by drowning and submersion in street/highway
U225.	All	[X]Intent self harm by drowning and submersion trade/service area
U226.	All	[X]Int self harm by drowning and submersion indust/construct area
U227.	All	[X]Int self harm by drowning and submersion occ farm
U22y.	All	[X]Int self harm by drowning and submersion other spec place
U22z.	All	[X]Intent self harm by drowning and submersion unspecif place
U23..	All	[X]Intent self harm by handgun discharge
U230.	All	[X]Int self harm by handgun discharge occ home
U231.	All	[X]Intent self harm by handgun discharge at res institut
U232.	All	[X]Int self harm by handgun discharge in school/pub admin area

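### The Parasuicide code list has 13 drug-specific overdose codes in Read V2, none in CTV3 and 8 in SNOMED, so capture of medication overdose depends on the coding system

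*Combined protocol and SAP*

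**What the plan says.** All references are to the combined protocol and SAP.

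- **Table 1, secondary outcomes (Stream 1).** Suicide attempt is defined as "Any episode of suicide attempt and suicide related codes, including deliberate medication overdose". The footnote sends the reader to appendix tables labelled s3 to s5, and no tables carry those labels. The mental health code table that does exist, sTable 2.1, has no suicide or self-harm block.
- **sTable 2.3.** Self-harm is mapped to ICD-10 X60-X84 and described as "Any diagnostic or indicative code for any form of self-harm, including suicide attempt".
- **Appendix 3.** The Read and SNOMED suicide codes are under "sTable 3.1 Read and SNOMED codes to be used to identify quality of life", in the Parasuicide block. The Read V2 part has a run of drug codes that starts at "Suicide and selfinflicted poisoning by analgesics, antipyretics and anti-rheumatics" (TK00), includes "Suicide and selfinflicted poisoning by other drugs and medicines" (TK04) and ends at "Suicide + selfinflicted poisoning by drug or medicine NOS" (TK05). The CTV3 part has the parent "Suicide and selfinflicted poisoning by solid and liquid substances" (TK0..) and then agent codes such as "Self poisoning by non-drug solid or liquid agents" (X71B0).
- **Stream 2, Study outcomes.** Parasuicide and deliberate self-harm are two components of the affective-symptoms indicator, alongside depression, low mood and suicidal ideation.
- **Matching and models.** Stream 1 matches within practice only where numbers permit. The Stream 1 Cox models and the Stream 2 count models adjust for age, gender, socioeconomic status, ethnicity and listed childhood conditions. Practice and coding system are in neither set.

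**The concern.** The three parts of the list should identify the same events, whichever coding system a practice used. They do not. The branch missing from CTV3 is the medication branch, which Table 1 names explicitly. The same overdose could therefore be an event in one practice and not in another because of the coding system alone.

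Two results are exposed. One is the parasuicide component of a Stream 2 quality-of-life indicator. The other is Stream 1's suicide-attempt outcome, if this list is used for it. Both streams report absolute incidence, which missed events lower directly. Relative measures are protected only if the compared groups have the same mix of coding systems and of overdose recording, and nothing in the plan secures that.

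**Working it through.** The plan gives no event count, sample size or sensitivity figure on this point, so there is no stated number to reproduce. The check is a count of entries.

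**Step 1. Drug-specific self-poisoning codes in the Parasuicide block**, matched by description to the Read V2 set:

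| Drug class (V2 stem) | Read V2 | CTV3 | SNOMED |
|---|---|---|---|
| Analgesics and related (TK00) | 1 | 0 | 1 |
| Barbiturates (TK01 and 7 subcodes) | 8 | 0 | 7 |
| Other sedatives and hypnotics (TK02) | 1 | 0 | 0 |
| Tranquillisers and psychotropics (TK03) | 1 | 0 | 0 |
| Other drugs (TK04) | 1 | 0 | 0 |
| Drug not specified (TK05) | 1 | 0 | 0 |
| **Total codes** | **13** | **0** | **8** |
| **Classes covered** | **6** | **0** | **2** |

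SNOMED therefore has 8 of 13 codes (5/13 = 38% absent) but 2 of 6 classes (4/6 = 67% absent).

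**Step 2. What CTV3 has instead.** Its entries for solid or liquid poisoning are TK0.., TK0z., TK06, TK07, TK08, X71B0, X71B1, X71B2 and XM1FX. The specific ones cover agricultural chemicals, corrosives, arsenic, non-drug agents, paraquat and plants. Generic entries remain: Xa04L (parasuicide), Xa3jI (unspecified attempt) and TK0... SNOMED also has generic codes for intentional self-poisoning (271982007) and self-administered poisoning (363293009).

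**Step 3. The [X] self-harm codes.** In both Read versions these run from U21 to U25 only: 5 stems x 11 codes = 55, covering hanging, drowning and three firearm groups. There is no self-poisoning stem, although sTable 2.3 covers any form of self-harm.

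**Step 4. Does CTV3's TK0.. bring in TK00 to TK05?** The documents do not say. Three features point against it:

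- CTV3 lists TK06, TK07, TK08 and TK0z. beside TK0.., which would be redundant if the parent included them.
- The entry All sits in the Term ID column, where other rows hold a single term identifier (J4103 with Y30D7, J4001 with Y30Fy). It appears to mean all terms of that code, not all its children.
- The IBDU list in sTable 1.1 contains J4.... If parents brought in children, the J40 Crohn's and J41 colitis codes would all be IBDU as well.

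**Step 5. Illustration only.** Let s be the share of attempts that are medication overdoses and f the share of those carrying only a drug-specific code. Neither is in the documents. Taking V2 capture as 100%, CTV3 capture = 1 - s x f:

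- s = 0.30, f = 0.25: 1 - 0.075 = 92.5%
- s = 0.50, f = 0.50: 1 - 0.25 = 75%
- s = 0.80, f = 0.90: 1 - 0.72 = 28%

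**Step 6. Effect on a ratio.** Let w be the share of a group's attempts arising in CTV3 practices, with full capture elsewhere. Then observed ratio = true ratio x (1 - w1 s1 f1) / (1 - w0 s0 f0). The error cancels when the products w s f are equal in the two groups. The documents give none of these quantities, so neither the direction nor the size of any bias in a ratio can be stated.

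**The case against.** The strongest objection is that listed parents may include their children, in which case TK0.. would largely close the CTV3 gap. There is some support for this, because the list does not enumerate children consistently. V2 has TK3.. without TK30 and TKx0. without TKx00, and CTV3 has TK1.. with none of V2's TK10, TK11, TK1y or TK1z. V2 also has a row described as [X] suicide, with an apparently clipped code, directly after the firearm codes; it could be a parent of the whole [X] block. So it cannot be argued that every child is spelled out. The features in step 4 still make the inclusive reading unlikely, and the plan should settle the matter.

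Three further objections limit the consequences.

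- **Stream 2.** A reader might infer that the Stream 2 primary objective is compromised. The documents do not support that. Parasuicide is one component of affective symptoms, and a person whose overdose is missed still counts if a depression or low-mood code is present.
- **Stream 1.** A reader might infer that the Table 1 outcome is certainly defined by this list. That is an inference from its being the only one. Table 1 points to mental health tables, sTable 2.3 is worded broadly enough to include overdose in any system, and algorithms for mental health outcomes are still to be developed. Suicide attempt is also a secondary outcome, outside the composite.
- **Unfinished appendix.** Many blocks are blank. The Parasuicide block is not: it is filled in for all three systems and reads as ready for use.

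Within-practice matching would tend to put Stream 1 cases and controls on the same coding. It is conditional, and Stream 2 has no matching.

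**Conclusion.** The point holds as an inequality between the three lists: 13 drug-specific codes in Read V2, none in CTV3, and 8 in SNOMED limited to analgesics and barbiturates. If the list is applied as written and parents do not bring in children, an overdose carrying only a drug-specific code is counted under V2, missed under CTV3, and counted under SNOMED for two of six drug classes. The effect is understated incidence for the parasuicide component in Stream 2 and, conditionally, for the secondary suicide-attempt outcome in Stream 1. Ratios may also be affected.

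Three stronger readings are tempting, and the documents do not support them.

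- **That SNOMED omits most of the codes.** It holds 8 of the 13. The shortfall is a majority only by drug class, and the two generic self-poisoning codes make its gap smaller than CTV3's.
- **That CTV3 practices lose every medication overdose.** Those recorded as TK0.., Xa3jI or Xa04L are kept.
- **That the loss can be given as a percentage.** The range of 28% to 92.5% capture in step 5 rests wholly on assumed inputs. The documents also do not say how many practices use each system, so no effect on a study estimate follows.

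The lists should be corrected, because the mismatch is plain on the page and cheap to remove.

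**What to change.** Before data extraction:

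1. Add to the CTV3 and SNOMED parts of the Parasuicide block the equivalents of V2 TK00 to TK05, where those systems have them.
2. Extend the [X] self-harm codes in both Read versions to self-poisoning, so that the list matches the X60-X84 scope of sTable 2.3.
3. State whether a listed parent code includes its children, for this block and the other code lists.
4. State which list defines the Table 1 suicide-attempt outcome, and correct the table reference in the footnote.
5. Before the outcome models are fitted, tabulate recorded attempts by method and coding system, to check that overdose capture is similar across systems.

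The cost is a revision of the code list and one descriptive table. It needs no new data and has no effect on patients.

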219166007		Suicide or self injury by scalding (navigational concept)
225050000		Drowning self (finding)
219333004		Drowning or immersion of unknown intent (event)
418765005		Exposure to potentially harmful entity, undetermined intent (event)
219328003		Hanging, strangulation or suffocation of unknown intent (event)
219329006		Hanging of unknown intent (event)
219330001		Suffocation of unknown intent by plastic bag (event)
219342006		Injury of unknown intent by sharp instrument (disorder)
Absence from school		
Read V2 Code	Term ID	Description
E2C10	All	School refusal
E2D2z	All	School refusal
13Z4J	All	School attendance poor

Eu912	All	[X]Truancy from school
E2C10	All	Unsocial childhood truancy
E2C20	All	Socialised childhood truancy
Read CTV3 Code	Term ID	Description
X766A	All	School refusal
13Z4J	All	School attendance poor
X7667	All	Intentional non-attendance at school
13Z4G	All	Left school free will
X7669	All	Parental withholding from school
X7668	All	Truancy
XE1Yt	All	Unsocial childhood truancy
E2C20	All	Socialised childhood truancy
SNOMED Code	Term ID	Description
248050007		Intentional non-attendance at school (finding)
248052004		School refusal (finding)
105479008		Truancy (finding)
248051006		Parental withholding from school (finding)
161131005		Left school free will (finding)
161133008		School attendance poor (finding)
440680000		Unable to attend school due to illness (finding)
31492004		Fear of school (finding)
271947006		School phobia (finding)
Unemployment		
Read V2 Code	Term ID	Description
13J7.	All	Unemployed
13J70	All	Recently unemployed

Read CTV3 Code	Term ID	Description
13J7.	All	Unemployed
13J71	All	Chronic unemployment
ZV620	All	[V]Unemployment
13R..	All	Unemployment benefits
13R1.	All	Unemployment benefit
13R2.	All	Redundancy payment
13RZ.	All	Unemployment benefit NOS
13JX.	All	Time off work
13JG.	All	Voluntarily redundant
13J3.	All	Loss of job
13J30	All	Sacked from work
13J8.	All	Redundant
13JJ.	All	Unfit for work
13JJ0	All	Benefit agency reports unfit for work
13JJ1	All	Benefit agency reports unfit for work but fit note no longer required
13Jk.	All	Not in employment, education or training
9DG4.	All	IB 113 DLS incapacity for work form paid
9DG2.	All	IB 113 DLS incapacity for work form sent
9DG3.	All	IB 113 DLS incapacity for work form received
9DG1.	All	IB 113 DLS incapacity for work form completed
9DQ3.	All	ESA113 form paid
9DQ1.	All	ESA113 form sent
9DQ2.	All	ESA113 form received
9DQ0.	All	ESA113 form completed
13OD.	All	Employment and support allowance

13J70	All	Recently unemployed
13J71	All	Chronic unemployment
ZV620	All	[V]Unemployment
XaPhf	All	Benefit agency reports unfit for work
Xabd4	All	Benefit agency reports unfit for work but fit note no longer required
13J8.	All	Redundant
13JG.	All	Voluntarily redundant
Ua2BD	All	Unfit to return to work
Ua2BE	All	Physically unfit for work
U12BF	All	Mentally unfit for work
13JX.	All	Time off work
XaZHu	All	ESA113 form paid
XaZHt	All	ESA113 form sent
XaZHs	All	ESA113 form received
XaZHj	All	ESA113 form completed
XaBhC	All	Employment and support allowance
XacJr	All	Not in employment, education or training
XE0pT	All	Loss of job
Ua0V9	All	Dismissed from job
Ua0VA	All	Unfair dismissal from job
XaCIW	All	IB 113 DLS incapacity for work form paid
XaCIU	All	IB 113 DLS incapacity for work form sent
XaCIV	All	IB 113 DLS incapacity for work form received
XaCIT	All	IB 113 DLS incapacity for work form completed
13JJ.	All	Unfit for work
13J6.	All	Medically retired

SNOMED Code	Term ID	Description
266956001		Loss of job (finding)
105496009		Dismissed from job (finding)
160901009		Made redundant (finding)
73438004		Unemployed (finding)
160900005		Chronic unemployment (finding)
160899000		Recently unemployed (finding)
354581000000101'		Unemployed person (person)
719401000000102'		Unemployed person (qualifier value)
224474004		Unfair dismissal from job (finding)
105498005		Voluntarily redundant (finding)
723481000000104'		Youth unemployment (qualifier value)
161005005		Unemployment benefits (qualifier value)
161006006		Unemployment benefit (qualifier value)
723971000000106'		Long term unemployment (qualifier value)
313083007		Unemployment counseling (procedure)
313084001		Redundancy counseling (procedure)
281559009		Number of days off work (observable entity)
160928004		Amount of time off work (observable entity)
439907006		Number of sick days off work in last month (observable entity)
105495008		Forced retirement, life event (finding)
925481000000108'		Benefits agency reports unfit for work but fit note no longer needed (finding)
161007002		Redundancy payment (qualifier value)
160910001		Unfit for work (finding)
374171000000109'		Benefits agency reports unfit for work (finding)
304248001		Unfit for particular post (finding)

22588002		Unfit to return to work (finding)
22589001		Mentally unfit to return to work (finding)
225889005		Physically unfit to return to work (finding)
224384002		Registered with job center (finding)
224385001		Registered with work placement officer (finding)
14121000000104'		IB113 DLS Incapacity for work form sent (finding)
14141000000106'		IB113 DLS Incapacity for work form paid (finding)
14131000000102'		IB113 DLS Incapacity for work form received (finding)
14111000000105'		IB113 DLS Incapacity for work form completed (finding)
835611000000109'		Employment and support allowance status (finding)
835641000000105'		Employment and support allowance 113 form completed (finding)
835711000000103'		Employment and support allowance 113 form paid (finding)
835691000000100'		Employment and support allowance 113 form received (finding)
835671000000104'		Employment and support allowance 113 form sent (finding)
957481000000103'		Not in employment, education or training (finding)
Absence from work		
Read V2 Code	Term ID	Description
Read CTV3 Code	Term ID	Description
SNOMED Code	Term ID	Description
IBD symptoms - abdominal pain		
Read V2 Code	Term ID	Description
Read CTV3 Code	Term ID	Description
SNOMED Code	Term ID	Description
IBD symptoms - discomforts or bloating		
Read V2 Code	Term ID	Description
Read CTV3 Code	Term ID	Description

SNOMED Code	Term ID	Description
IBD symptoms - diarrhoea		
Read V2 Code	Term ID	Description
Read CTV3 Code	Term ID	Description
SNOMED Code	Term ID	Description
IBD symptoms - weight loss		
Read V2 Code	Term ID	Description
Read CTV3 Code	Term ID	Description
SNOMED Code	Term ID	Description
IBD symptoms - tiredness/fatigue		
Read V2 Code	Term ID	Description
Read CTV3 Code	Term ID	Description
SNOMED Code	Term ID	Description
Growth retardation related codes		
Read V2 Code	Term ID	Description
Read CTV3 Code	Term ID	Description
SNOMED Code	Term ID	Description

sTable 3.2 Read and SNOMED codes to be used to identify the severity of IBD

Medication use		
Read V2 Code	Term ID	Description
Read CTV3 Code	Term ID	Description
SNOMED Code	Term ID	Description
Surgical intervention		
Read V2 Code	Term ID	Description
Read CTV3 Code	Term ID	Description
SNOMED Code	Term ID	Description
Hospital admissions		
Read V2 Code	Term ID	Description
Read CTV3 Code	Term ID	Description
SNOMED Code	Term ID	Description
Nutritional supplements (Modulen, Fortisip, Ensure, Osmolite, and Neocate)		
Read V2 Code	Term ID	Description
Read CTV3 Code	Term ID	Description
SNOMED Code	Term ID	Description
